¹⁸ The skeletal muscle CSAs will be determined at baseline, 6 months (mid-intervention) and 1 year after training (post-intervention). Both lower limbs will be strapped together using a soft Thera-band to avoid any movement inside the magnet. Participants will be instructed to lie still inside the magnet and they will be provided with earplugs to protect their ears against the magnet noise. The duration of the whole scan including the preparation time should not exceed 10 minutes. Images of both thighs will be collected using the following scanning parameters (repetition time, 500; echo time, 14; field of view, 20cm; matrix, 256×256). Transaxial images, 8 mm thick and 4 mm apart, will be taken from the hip joint to the knee joint using a localized coil. Images will be downloaded and analyzed using X-vessel software.^{17,19,20, 31,55}

Testosterone and PSA Concentration. The serum testosterone concentration and PSA levels will be measured at the beginning, every 4 weeks and 1 year after intervention. IV line will be placed after overnight fast, serum total T and PSA concentrations will be measured in duplicates.⁷⁸ Samples will be sent for analysis using a standard procedure assays.

Specific Aim 2. We will determine the association between the changes in skeletal muscle size, IMF, leg lean mass and the metabolic profile as determined by measuring basal metabolic rate (BMR), lipid panel and carbohydrate profile. Participants will undergo an array of metabolic measurements at baseline, 6 and 12 months post-interventions including BMR, fasting lipid panel and 3 hour IVGTT. Other metabolic and inflammatory biomarkers (plasma IGF-1, IGFBP-3, TNF-alpha, IL-6 and CRP) will also be measured at the 3 time points. We hypothesize that the increase in lean mass following TRT+ LPWS will increase BMR and improve both carbohydrate and lipid profiles as well as associated with decrease in FFA and inflammatory biomarkers.

BMR and respiratory exchange ratio. After an overnight fast, participants will be kept in a dark room for 20-30 minutes to attain a resting state during which BMR will be measured by using a canopy. The gasses (VCO₂ and VO₂) collected will used to determine the respiratory exchange ratio. This will help to determine the changes in the percentage of substrate utilization (% fat vs. % carbohydrate) after the interventions.¹⁵

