Serum total, free testosterone and IGF-1. The plasma T and IGF-1 will be measured in the morning (2 ml/ sample).^{78,79} The analysis of total T will be performed by radioimmunoassay after sample extraction and column chromatography. The interassay coefficient of variation (CV) is 12.5% or less for all quality control samples analyzed. Plasma IGF-I and IGFBP-3, concentrations will be measured by immunoluminometric assay (Quest Diagnostics, Madison,

NJ) and RIA (Diagnostics Systems Laboratories Inc., Webster, TX), respectively. Intra-assay precision of IGF-1 is 4.6% at 50 ng/ml and 3.6% at 168 ng/ml.

Blood lipids. Each subject will have fasting lipid profiles (HDL-C, LDL-C, total cholesterol, and TG) assessed, with total cholesterol: HDL-C ratios utilized as the criterion variable. Concurrent with the IVGTT and following a 12-hour fast, 10 ml of blood will be collected from the indwelling venous catheter and lipids determined by standard analyses procedures.¹⁵

Inflammatory biomarkers. Before starting the IVGTT and following a 12-hour fast, 10 ml of blood will be collected from the indwelling venous catheter and CRP, IL-6, TNF- α , and FFA will be determined by standard procedures using commercially available assay kits.²¹

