centrifuged to separate the chloroform and aqueous phases. mRNA will be extracted using commercially available kits. Residual genomic DNA will be removed by on the column DNAse I digestion. cDNA libraries will be synthesized by reverse transcription of total RNA using commercially available kits. Expression of individual target genes (IGF1, PGC1alpha, AMPK, Akt, mTOR) will be evaluated by qPCR using 18S RNA or housekeeping genes as loading controls. The effects of interventions on mRNA expression levels will be expressed as fold-change where fold change is calculated using the 2^{-ΔΔCt} method.^{74,83}

Mitochondrial ETC activities. The assays will be performed using fresh cholate-treated skeletal muscle homogenates. ETC complex activities will be measured spectrophotometrically as specific donor-acceptor oxidoreductase activities in 0.1M phosphate buffer (HP 8453 and Lambda 35 UV/VIS). Rotenone-sensitive NADH cytochrome c reductase will measure complexes I and III. NADH coenzyme Q reductase will be measured as the rotenone-sensitive oxidation of NADH with decylubiquinone as acceptor, and assesses complex I. NADH ferricyanide reductase measures NADH dehydrogenase in complex I. Cytochrome c oxidase will be measured as the first order rate constant.^{42,43} Flurometric measurements will be conducted to measure the oxidative and glycolytic enzymes' activities including citrate synthase and SDH.^{42, 43, 76}

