Statistical Analyses. Means and standard deviations or frequencies and percentages will be reported for all data. Similar summaries will be provided for all outcome and biomarker data separately at baseline, 6-, and 12-months. A repeated-measures ANOVA will be used to analyze the primary study outcome, skeletal muscle size, with treatment, time, and the interaction of these variables included in the model. A first order autoregressive correlation structure will be used to capture the dependency within subjects' outcomes. A specific contrast will be used to determine if the change from baseline for the treatment group is different than that of the control group. A model selection procedure will be performed due to the relatively large number of predictor variables compared to the number of subjects for specific aims 2 and 3. A penalized random effect model will be used to suggest the important predictors for each outcome separately. These include each specific predictor mentioned in the specific aims as well as injury characteristics.⁸⁴ A parsimonious model will be chosen by the Bayesian information criterion. Since the aforementioned model is well-suited for model selection, but results in biased parameter estimates, an unpenalized random effects model will be fitted based on the parsimonious model and used for inference. Study period will be included in all analyses, and a time by group interaction will be included for the analyses associated with Specific Aim 3. All statistics will performed with R (3.3.0) with the 'glmmLasso' package. Prior to any statistical analysis, any of the biomarkers may be transformed to ensure all statistical assumptions are met. A simulation study was used to determine the power achieved from the proposed study if 5% of subjects were assumed to drop out at the 12-month observation point. One thousand datasets were created with Cohen's d varying between 0.5 and 2.0, with the anticipated 24 subjects being equally allocated to the treatment and control groups and the subjects' outcomes having a correlation of 0.25. A linear mixed-effects model was used to analyze the simulated data using a one-sided test at α =0.05. Results of the study show that this design will have the power to detect differences of d=1.28 with 80% power and d=1.48 with 90% power. An intent-totreat approach will be used to deal with missing data. If the missing data is due to drop-out, the statistical methods are valid as long as the data mechanism is considered missing at random or missing completely at random.

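### Aims 2 and 3: predictors selected by penalized model and BIC are tested by refitting the same data, so the p-values and intervals of the selected predictors are not valid at nominal level

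*Combined protocol and SAP*

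**What the plan says.** All of this is in section 4, Research Design and Methods, under Statistical Analyses.

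- Selection is used because of the "relatively large number of predictor variables compared to the number of subjects for specific aims 2 and 3".
- The selection step runs outcome by outcome: "A penalized random effect model will be used to suggest the important predictors for each outcome separately". The candidates are the predictors named in the aims plus injury characteristics. Their number is not given.
- BIC then picks a parsimonious model. Neither its sample size (participants or observations) nor the fit at which it is computed is stated.
- The reason given for refitting is that penalized estimates are biased. The text concludes that "an unpenalized random effects model will be fitted based on the parsimonious model and used for inference".
- Two kinds of term stay in regardless of selection: study period in all analyses, and, for the third aim, "a time by group interaction will be included for the analyses associated with Specific Aim 3".

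The primary outcome has its own repeated-measures ANOVA with no selection step. The text available for review names no sample split, hold-out data, selection-adjusted method or resampling of the whole procedure, and no exploratory label. No alpha is given for Aims 2 and 3.

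**The concern.** A predictor survives the penalized step because it looks large in these data. Testing it again on the same data, as if it had been named in advance, counts the same evidence twice. Unpenalized refitting answers the shrinkage problem that the plan identifies and leaves the selection problem untouched.

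This matters most for Aim 2, which is itself about associations: "We will determine the association between the changes in skeletal muscle size, IMF, leg lean mass and the metabolic profile". There the selected coefficients are the result, not an adjustment. Section 5, in the recruitment timeline, plans three manuscripts on the specific aims, so the refitted p-values would reach print as inference from 24 men.

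**Working it through.** **1. The plan's own figure.** The only computed figure in this text is power for the group comparison. Inputs: 12 men per arm, 5% dropout at month 12 (12 × 0.95 = 11.4 per arm), "outcomes having a correlation of 0.25", one-sided 0.05.

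- SD of change = √(2 × (1 − 0.25)) = 1.225; standard error = √(2/11.4) = 0.419 SDs of change.
- d = 1.28: 1.28/1.225/0.419 = 2.495; Φ(2.495 − 1.645) = 0.802.
- d = 1.48: 1.48/1.225/0.419 = 2.885; Φ(2.885 − 1.645) = 0.893.

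The stated 80% and 90% are reproduced. They say nothing about the selected predictors, for which the plan gives no figure.

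**2. Analytic check.** For a single candidate scored on unpenalized fits, BIC admits it only if its 1-df chi-square exceeds ln(n).

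- n = 72 (24 men × 3 visits): ln 72 = 4.28, i.e. p < 0.039. Anything admitted is already below 0.05.
- n = 24: ln 24 = 3.18, i.e. p < 0.075. About 0.05/0.075 = 67% of admitted nulls are below 0.05.

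**3. Simulation of the procedure.** From the plan: 24 men, 3 visits, 5% month-12 dropout, correlation 0.25. Assumed: 5, 10 or 19 candidates, predictor correlation 0 or 0.5, a second outcome correlation of 0.7, and two-sided 5% tests. The lasso was coded directly and is not the glmmLasso package. BIC was taken at the penalized fit, followed by an unpenalized refit.

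| Quantity | BIC n = 72 | BIC n = 24 |
|---|---|---|
| All null: any predictor selected | 8-12% | 18-26% |
| All null: selected predictors with p<0.05 | 82-92% | 66-75% |
| All null: at least one p<0.05 per outcome | 8-12% | 16-25% |
| One real predictor among 10: selected nulls with p<0.05 | 38-90% | 34-67% |
| One real predictor among 10: at least one null with p<0.05 | 10-22% | 20-31% |

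The real predictor, when selected, was estimated at the following multiple of its true value:

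| True effect (SD per SD) | Estimate/truth | Coverage of the nominal 95% interval |
|---|---|---|
| 0.15 | 2.0-2.5 | 66-85% |
| 0.25 | 1.3-1.6 | 87-95% |
| 0.35 | 1.0-1.2 | 94-97% |
| 0.5 | 0.9-1.0 | 90-96% |

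**4. Independent re-run.** Separate code with 6 to 20 candidates and time and time-by-group forced in gave 83-91% of selected nulls at p<0.05 with n = 72, and 69% with n = 24. Nominal 95% intervals with n = 72 covered zero in only 9-17%. With two real effects of 0.3 among 15 candidates the share was 45%, and the real effects were overestimated by 24%. A smaller run (300 per cell, variance treated as known) gave 22-54% beside a real effect of 0.5-0.7.

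**5. Is data reuse the cause?** When the selected model was tested on a fresh sample of the same size, the rate for selected nulls fell to 4.5-7%.

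**6. Forced term.** Aim 3's time-by-group test rejected in 4-7% of null trials, close to nominal.

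**7. Sensitivity to BIC scoring.** If BIC is scored on unpenalized refits along the path, at least one false-significant predictor appears in 20-61% (n = 72) or 25-72% (n = 24) of all-null trials.

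**The case against.** The strongest reply is that the overall error rate is modest. With n = 72 the procedure gives 8-12% false findings per outcome, while three unselected, unadjusted predictors give 13-17%. Averaged over all candidates, a given null ends up significant in only 0.7-4.5% of trials. This stands: a reader might infer that selection produces more false findings than a plain unadjusted model, and with BIC taken at the penalized fit and n = 72 the figures do not support that. It does not rescue the reported p-values, because only the survivors are reported, and theirs are the ones that fail.

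Second, the highest shares need every candidate to be null, and the plan's preliminary data suggest otherwise. Item d reports that lean-mass gain explained 51% of the variance in BMR (r = √0.51 = 0.71). Item f reports r = 0.74-0.84 between muscle area and mitochondrial enzyme activity. Those samples are small (22, 16 and 14), and the BMR data come from a trial that excluded men who did not respond to stimulation, so the values may not carry over. Still, where a strong predictor exists its own estimate is hardly distorted, and the share for selected nulls is lower, though far above 5%.

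Third, the size rests on assumed candidate numbers and correlations and was not run in the planned package. That also stands. The direction was the same in every scenario; the exact size is not established.

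**Conclusion.** The point holds for the selected predictors: in practice the Aim 2 associations, and any covariates selected in Aim 3. Their refitted p-values and intervals ignore the selection. Against a nominal 5%, about 66-92% of selected nulls show p<0.05 if all candidates are null, and about 34-90% beside one real predictor of 0.15-0.5 SD per SD; stronger real effects can give lower shares. Weak real effects are overestimated when selected (about 1.3-1.6 times at 0.25), but not at 0.5. These sizes rest on the assumed candidate sets and on BIC at the penalized fit.

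Two stronger readings are tempting and not supported. One is that the trial's main result, or Aim 3's group comparison, is compromised: the muscle-size contrast involves no selection, and the time-by-group term is forced in and stayed near nominal. The other is that a significant selected predictor is usually false, or always inflated: the figures describe null predictors that were selected, not the chance that a selected predictor is null.

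Whether visit levels or changes enter the Aim 2 models is not stated. That is a separate clarification, which matters only if levels enter, and this conclusion does not depend on it. The matter should be fixed before analysis, but it does not threaten the primary comparison.

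**What to change.** In Statistical Analyses:

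1. Replace the statement that the refit serves inference. Say that predictors selected by the penalized model and BIC in Aims 2 and 3 are exploratory and are reported without p-values or nominal confidence intervals. Any uncertainty shown should come from a method that accounts for selection, for example a bootstrap that resamples whole participants and repeats the full selection, reported as selection frequency and spread of the estimates.
2. State the BIC sample size (participants or observations) and the fit at which BIC is computed.
3. If confirmatory Aim 2 tests are wanted, fit one unselected model per outcome with muscle size, IMF and leg lean mass, for a few outcomes named in advance, with Holm across all tests. For lipids the plan already has a candidate, "with total cholesterol: HDL-C ratios utilized as the criterion variable". Three predictors by three outcomes make 9 tests. In simulation, Holm held the chance of any false finding at 3.7-5.1%, against 28.5-35.5% unadjusted.

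**Cost.** SAP wording and a little code; no new data or visits. There will be fewer nominally significant associations and less power per test. With about 71 rows (72 less 5% of 24), residual df = 71 − 24 − 2 − 3 = 42. Using a noncentral t with noncentrality √43 × r/√(1 − r²), the within-man partial correlation detectable with 80% power is 0.40 for one test and 0.50 at 0.05/9. Overlap between the muscle measures costs more. If two of them correlate 0.8 and each correlates 0.5 with the outcome (assumed), the partial correlation is (0.5 − 0.8 × 0.5)/√((1 − 0.64)(1 − 0.25)) = 0.19, well below what is detectable.

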Testosterone (T) is an anabolic and androgenic hormone that is associated with growth. The majority of testosterone production takes place in the Leydig cells of the testes. Approximately 60-70% of testosterone is tightly bound to sex hormone binding globulin (SHBG), 30-40% is bound loosely to albumin, and 0.5-2% is free.⁶³⁻⁶⁷ Sixty percent of men with SCI have low T levels in the first six months after SCI.⁶³ A previous study demonstrated a 37% lower level of T in men with tetraplegia compared to AB controls.⁶⁵ Testosterone signaling through the androgen receptor also results in increased brain-derived neurotrophic factor expression and restored the withdrawn synapses in acute models with peripheral denervation. 68-69 The use of an androgen receptor antagonist blocks the effects of exercise on the regenerative capacity after LMN, emphasizing the significance of using testosterone replacement therapy (TRT) in promoting axonal growth and restoring muscle size.⁶⁸⁻⁶⁹ The effect of TRT on cardiovascular risk has been controversial.^{70,71} There are data showing that hypogonadism is a risk for cardiovascular disease.⁷⁰ Some replacement studies show increased risk, but another study showed decreased mortality in veterans receiving testosterone.⁷¹ One study in older men reported that injectable testosterone may be associated with increased cardiovascular risk but topical testosterone was not. 72 Based on the available scientific evidence, we felt that application of transdermal patches is the more feasible and safe approach for persons with SCI.

Rationale for using TRT following denervation. TRT is an FDA-approved therapy used to treat hypogonadism and often results in significant improvement of muscle strength and fat-free mass in hypogonadal men. In rats with complete SCI, TRT has been shown to attenuate muscle atrophy and the decline in oxidative and glycolytic enzymatic activities.⁶⁶ Transdermal TRT of 5-10 mg/day has been shown to increase lean mass and basal metabolic rate (BMR) in hypogonadal men with SCI.⁶⁷ In an acute denervation model, TRT acts on the nervous system using two different mechanisms, genomic and non-genomic. The genomic mechanism involves binding of the hormone to its nuclear receptor. The non-genomic mechanism is fast-driven and involves interaction of the hormone with membrane or neurotransmitter receptors. This leads to

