The goal of this randomized prospective controlled study is to investigate the effects of one year of TRT+LPWS versus TRT+standard NMES on muscle size (primary outcome variable), leg lean mass and percentage IMF, metabolic profile (BMR, carbohydrate and lipid profile) and protein synthesis and degradation pathways as well as mitochondrial health. The long-term goal is to develop a rehabilitation strategy to mitigate the deleterious changes in muscle size and lower leg lean mass in persons with denervation following SCI.

Subjects. 24 chronic (1 year or more post-injury) individuals with motor complete SCI will be recruited from the Hunter Holmes McGuire VA Spinal Cord Dysfunction registry (n=~1,717-1800) and Virginia Commonwealth University (n=750-1000) over 4 years. The Spinal Cord Injury and Disorders Outcomes (SCIDO) for FY2105 suggests that there are ~ 20% of our outpatient evaluation with LMN denervation as result of SCI. Approved flyers and advertisements will also be posted at the VAMC, VCU Hospitals and clinic sites. Training will be conducted twice weekly using a progressive RT model described in preliminary studies and previously by our group.⁵⁵.

Inclusion. All participants will be between 18-70 years old, male, and greater than one-year post SCI. The age upper limit was set at 70 years to reduce the likelihood of developing any cardiovascular side effects from using TRT. Participants must have traumatic complete or incomplete T10 SCI or below (AIS A or B; i.e. motor deficit below the level of injury) with denervation of both knee extensor muscles and tolerance to the LPWS paradigm.

Exclusion. Participants with the following pre-existing medical conditions will be excluded: cardiovascular disease, uncontrolled type II DM, (HbA1c >7.5), uncontrolled hypertension (resting blood pressure >140 /90 mmHg), and those on insulin, or who have pressure sores greater than stage 3, hematocrit above 50% or severe urinary tract infection. Those with a hyper-physiological testosterone level (above 800 ng/dl) will and those who fail to tolerate the LPWS paradigm will also be excluded. Lower extremity fracture around the knee joint within the last 2 years will be excluded. After signing a consent form, all participants will undergo knee DXA scans and knee bone mineral density (BMD) less 0.6 gm/cm² or hip BMD T-score below - 3.5 will result in exclusion from the study to prevent fracture at the distal femur or proximal tibia during training.

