including HbA1c, as well as lipid panels, CRP, IL-6, TNF-alpha, and free fatty acids (FFA). This will be followed by a 3-hour intravenous glucose tolerance test (IVGTT) which will begin at 8 AM and terminate at 11 AM. During the IVGTT, a dietitian will meet with each participant individually to ensure that they will follow a standard diet pattern during the 1 year-intervention (45% carbohydrate, 35% fat and 25% protein) to avoid any confounding effects on our measurements. All participants will be asked to maintain a **3 day food record** monitoring their energy intake during the course of the study. The diaries will be evaluated weekly by the dietitian to provide monthly feedback. All participants will meet with the dietitian three times during the study to ensure appropriate adherence to the diet pattern throughout the study. The vastus lateralis muscle will be biopsied to measure protein expression and to determine mitochondrial enzymatic activities.^{75, 76}

Twenty-four participants will be randomly assigned to either one year of TRT+LPWS (n = 12) or a TRT+ standard NMES (n = 12). Testosterone patches (Tp; 4

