Specific Aim 3. We will investigate the cellular mechanisms responsible for evoking skeletal muscle hypertrophy following TRT+LPWS compared to TRT+ standard NMES. Participants will undergo 3 muscle biopsies of vastus lateralis at baseline, 6 and 12 months post-intervention to measure gene and protein expression and perform mitochondrial enzymatic assays. Considering the limited muscle tissue in persons with denervation atrophy, four biopsy samples of the vastus lateralis muscle (total: 25-50 mg wet wt) will be obtained by a 14 gauge Tru-Cut needle using a sterile technique and local anesthesia (2% lidocaine). The biopsy samples will be frozen in liquid nitrogen and stored at -70C until further analysis. We hypothesize that the TRT+LPWS will upregulate protein synthetic and downregulate protein degradation pathways, gene expression and mitochondrial enzymatic ETC activities compared

to the TRT+ standard NMES group.

Protein content. Muscle biopsy samples will be homogenized on ice using the appropriate buffers. Equal amounts of protein will be resolved by SDS-PAGE after which proteins will be electrophoretically transferred to a PVDF membrane. Western blot analysis will then be performed to determine the protein concentrations as described in preliminary data and previously by our lab.⁷⁵ After blocking, membranes will be probed with primary antibodies for activated pathways including AMPK, p-AMPK PGC-1α, IGF-1, Akt, p-Akt, mTOR and protein degradation pathways (FOXO1/3, atrogin-1, MURF). followed by incubation with the appropriate secondary antibody. Western blots will be quantified by scanning with A GS800 densitometer. Optical densities of the Western blots will be measured using image-analysis software (Molecular Analyst; Bio-Rad).

Real-time quantitative PCR (qPCR). Quantification of mRNA levels by RT qPCR (real-time PCR) in muscle biopsy samples will follow well-established procedures in our lab. Briefly, frozen muscle biopsy samples will be added to Trizol reagent and immediately homogenized then

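### The goal promises a between-arm effect of TRT+LPWS on metabolic profile, but no between-arm comparison is specified for the Aim 2 metabolic outcomes

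*Combined protocol and SAP*

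**What the plan says.** The opening of section 4 (Research Design and Methods) gives the goal as follows: "investigate the effects of one year of TRT+LPWS versus TRT+standard NMES on muscle size (primary outcome variable), leg lean mass and percentage IMF, metabolic profile", with BMR, carbohydrate and lipid measures listed under the last item.

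Specific Aim 2 restates the metabolic part as a correlation: "We will determine the association between the changes in skeletal muscle size, IMF, leg lean mass and the metabolic profile". Its hypothesis is "that the increase in lean mass following TRT+ LPWS will increase BMR and improve both carbohydrate and lipid profiles", with no comparator. The Specific Aim 3 hypothesis, by contrast, is framed as a comparison "to the TRT+ standard NMES group".

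The Statistical Analyses paragraph specifies:
- for muscle size, treatment, time and their interaction, with a contrast of change from baseline between arms;
- for Aims 2 and 3, a penalised random effects model, selection by BIC, then an unpenalised refit. Candidate predictors are those named in the aims plus injury characteristics;
- study period in every analysis, but "a time by group interaction will be included for the analyses associated with Specific Aim 3".

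Both arms receive testosterone for the year (Testosterone replacement Therapy paragraph and Specific Aim 1). Section 1 says that transdermal testosterone "has been shown to increase lean mass and basal metabolic rate (BMR) in hypogonadal men with SCI".

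**The concern.** A randomised control arm exists and has the same metabolic tests at baseline, 6 and 12 months, yet no specified analysis uses it for the metabolic outcomes. An association between muscle change and metabolic change, taken over all 24 men, answers a different question from whether TRT+LPWS improves metabolic profile more than the control does.

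The surrounding text makes an uncontrolled reading likely. Section 1 expects one year of the combination to improve metabolic profile by 20% to 30%, without reference to control, and section 8 describes each man as acting as his own control. Testosterone is common to both arms and, on the documents' own account, can move both the Aim 2 predictor (lean mass) and an Aim 2 outcome (BMR). At stake is whether a stated objective has a valid prespecified test, or whether any between-arm result would be chosen after the data are seen.

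**Working it through.** **1. Objective against analysis**

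| Outcome | Between-arm goal in section 4? | Group-by-time term specified? |
|---|---|---|
| Muscle size (primary) | yes | yes, with a contrast of change |
| Metabolic profile (Aim 2) | yes | no |
| Protein, gene and mitochondrial measures (Aim 3) | yes | yes |

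One sentence covers all analyses for study period and then confines the interaction to Aim 3. The predictors that the Aim 2 objective names are muscle size, IMF and leg lean mass. A group term, if offered at all, could be dropped by BIC.

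**2. What the stated power refers to**

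Inputs from Statistical Analyses: 24 men, 12 per arm; correlation 0.25; one-sided α=0.05; 5% dropout, so 12 × 0.95 = 11.4 per arm. The plan claims 80% power at d=1.28 and 90% at d=1.48.

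For a between-arm contrast of change, the SD of change is √(2(1−0.25)) = 1.225 and the noncentrality is (d/1.225)/√(2/n).

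| d | noncentrality, n=12 | power, t, 22 df | noncentrality, n=11.4 | power, t, 44 df | power, z |
|---|---|---|---|---|---|
| 1.28 | 2.56 | 0.798 | 2.50 | 0.792 | 0.802 |
| 1.48 | 2.96 | 0.889 | 2.88 | 0.884 | 0.893 |

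The plan's figures reproduce as a between-arm contrast of change, which is the contrast that Aim 2 lacks. At d=1.28 and n=12, a two-sided test has power 0.687.

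**3. What the Aim 2 association can show when LPWS has no metabolic effect**

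Simulation, 24 men, three visits with weights w = 0, 0.5, 1:
- muscle = subject effect + error + w(c + rᵢ + 1.28 × group)
- metabolic outcome = subject effect + error + w(c + rᵢ)

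Subject variance is 0.25 and error variance 0.75, which gives the plan's correlation of 0.25. Here c is a shift common to both arms (0, 0.8 or 1.28 SD) and rᵢ is a man's own response to testosterone, shared by muscle and metabolism, with SD h. Both c and h are assumptions. The analysis regressed the metabolic outcome on muscle and visit within subject, one-sided at 0.05, in 1,000 trials per cell. It omits the penalised selection step and dropout.

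| h | c=0 | c=0.8 | c=1.28 |
|---|---|---|---|
| 0 | 0.059 | 0.053 | 0.052 |
| 0.5 | 0.119 | 0.111 | 0.146 |
| 1.0 | 0.494 | 0.496 | 0.458 |

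Monte Carlo error is about √(0.05×0.95/1000) = 0.007 in the first row and √(0.5×0.5/1000) = 0.016 in the last. A uniform shift (h=0) produces no excess. Varying responses do: the association is then real within men, but it comes from testosterone and says nothing about LPWS.

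**4. The between-arm contrast under the same null**

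With common shifts from 0 to 1.28 SD in both arms (h=0) and no LPWS effect, the one-sided contrast of change was positive in 4.6% to 5.2% of 5,000 simulated trials per shift. The shared shift cancels.

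**The case against.** The strongest defence is that Aim 2 is an association question by design and that study period is in its model. The second part stands: a uniform shift from testosterone, or from anything else common to all men, does not distort the association coefficient, as the h=0 row shows. The first part does not rescue the section 4 goal, which is comparative.

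A second defence is that the omission is one of silence. The plan does not forbid a group comparison, visit summaries are planned, and since the Aim 2 hypothesis mentions TRT+LPWS, group might count as a predictor named in the aims. That is fair, but a term open to BIC selection is not a prespecified contrast of change.

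Third, the testosterone evidence cited in section 1 concerns hypogonadal men. This trial has no low-testosterone entry criterion, and in the team's earlier trial only 18% were below 300 ng/dl at baseline. The size and spread of any response are therefore assumptions.

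A reader might go further and infer that the plan would declare a metabolic benefit from before-after change. The documents do not support that: Statistical Analyses contains no paired or within-arm test and does not say that Aim 2 inference comes from the period coefficient. A reader might also infer that the dietitian's advice starts a new diet at baseline and biases later values. The protocol presents the diet as a standard pattern meant to avoid confounding and does not say how it differs from what the men already eat. It applies to both arms, so the randomised contrast balances it. No diet lead-in is needed.

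**Conclusion.** The point holds as a mismatch between objective and analysis: a between-arm goal for metabolic profile has no prespecified between-arm test. This follows from the text and needs no assumption. A period effect, a within-arm change or a pooled association cannot be attributed to LPWS while both arms take testosterone.

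The size of the problem for the association does rest on assumptions. It is nil for a uniform response. Significant associations unrelated to LPWS occur in about 11% to 15% of trials at a response SD of 0.5, and 46% to 50% at 1.0. These are results for a simplified version of the planned model, not error rates of the trial. The primary outcome is unaffected, since it already has the right contrast. The change should be made, but the validity of the main result does not depend on it.

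**What to change.** In Statistical Analyses, add for three key Aim 2 outcomes (BMR, insulin sensitivity from the IVGTT, and the total cholesterol:HDL-C ratio, which the protocol already names as its lipid criterion) a model with treatment, time and treatment-by-time forced in and exempt from BIC selection. Judge the effect of TRT+LPWS by the between-arm difference in change from baseline to 12 months. Keep the muscle-metabolism association as a separate question, labelled exploratory.

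The cost is a few lines of text. Both arms already have these tests at all three visits, so no new data are needed. The drawback is precision: on the plan's own assumptions (one-sided 0.05, correlation 0.25) the contrast has 80% power only near d=1.28. If individual responses of SD 0.5 to 1.0 add to the variance of change, that becomes 1.28 × √(1.75/1.5) = 1.38 to 1.28 × √(2.5/1.5) = 1.65. Three outcomes each tested at 0.05 without adjustment would, if independent, give a chance of 1 − 0.95³ = 0.14 of at least one false positive. They should therefore be reported as secondary, with estimates and confidence intervals, and a non-significant result should not be read as no effect.
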